**Table 9: Assessment of Adherence to Follow-Up Recommendations**

Recommended Follow-up	Number of visits per year considered adherent to recommendations
1-2 months	At least 6 visits per year with an eye care provider
3-6 months	At least 3 visits per year with an eye care provider
6 months	At least 2 visits per year with an eye care provider
12 months	At least 1 visit per year with an eye care provider

E.2.c. Primary Analysis for Aim 2: The primary outcome of the study is adherence to recommended follow-up in each year as described in section E.1.c. For each of the 3 years of follow-up, we have a dichotomous measure of adherence. We will model this longitudinal dichotomous outcome using Poisson regression within a generalized estimating equation (GEE) framework. Our model will include time (Year 1, 2, and 3), randomization assignment, randomization by treatment interaction, and baseline individual characteristics believed to be associated with adherence to follow-up, including age, diagnosis, vision impairment, and overall vision-related quality-of-life. Within this model, we will test 2 hypotheses.

First, we will compare randomization groups at Year 1 to test whether there are differences in early adherence. Second, we will calculate the average effect of randomization across Years 2 and 3 and test the long-term efficacy of the intervention. In both cases, we will estimate the overall relative risk of adherence along with its associated confidence interval. Each test will be performed with alpha=0.025. The primary analysis will include all patients who were randomized and have some adherence data (see section on missing data below).

E.2.d. Power for the Primary Analysis for Aim 2: Our estimated available sample size is given in Figure 2. We will randomize 300 patients (150 per group). Assuming up to 10% dropout where adherence cannot be calculated due to death or study withdrawal (i.e., final analysis dataset of n=135 per group), we calculate power to detect a 20% improvement in adherence under various assumptions of adherence under Usual Care. We have greater than 80% power to detect these differences using a two-sided chi-square test with alpha=0.025 (Table 10).

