**Table 6: Summary Benchmarks Preferred Practice Pattern Guidelines for POAG**

Target IOP Achieved	Progression of Damage	Duration of Control (months)	Appropriate Follow-up Interval (months)
Yes	No	<6	6
Yes	No	>6	12
Yes	Yes	NA	1-2
No	Yes	NA	1-2
No	No	NA	3-6

Source: *American Academy of Ophthalmology*

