## **E.2. Data Analysis for Aims 1 and 2**

**E.2.a. Primary Analysis for Aim 1:** The primary analysis for Aim 1 will be to estimate the positive predictive value (PPV) of the teleophthalmology intervention for diagnosing of glaucoma. We hypothesize that the diagnosis of glaucoma and glaucoma suspect using undilated optic disc images, tonometry pressure results, and medical history will predict the comprehensive eye exam diagnosis. That is, we will calculate the proportion of patients diagnosed with glaucoma or glaucoma suspect whose diagnosis was confirmed at Visit 2 with an exact two-sided binomial confidence interval. We will conclude that the telemedicine intervention has good performance if the lower bound of the confidence interval is above 80%.

The expected sample size for this aim is 250 patients as we anticipate approximately 50% of those diagnosed with eye pathology and who return for the confirmation Visit 2 will have been diagnosed with glaucoma or glaucoma suspect at Visit 1. Data from Maa (2014) can be used to estimate the PPV for glaucoma at 85%. With 250 patients, we have 50% power to conclude the PPV is greater than 80% if the true PPV is 85% and over 99% power to conclude the PPV is greater than 80% if the true PPV is 90% using a 2-sided test with alpha=0.05. We will repeat this analysis looking at the proportion of patients diagnosed with eye pathology who in fact have an ocular diagnosis (whether or not the exact abnormality was correct).

**E.2.b. Primary Outcome Measure for Aim 2:** Patient baseline demographic and clinical characteristics will be summarized overall and by randomization assignment (in Aim 2) using means, medians, standard deviations, and ranges or frequencies and percentages, as appropriate. Our general approach from the randomized trial is to analyze patients as randomized regardless of the amount of intervention received. The primary outcome measure for Aim 2 is attendance at recommended follow-up visits (Visit 4 and later). Since the expected

number of appointments will differ based on diagnosis and disease severity, which may change over time, attendance will be summarized annually.

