For each year under observation, an expected number of visits will be determined based on the recommended follow-up at the first visit for that year (Table 9). For purposes of this calculation, attendance at appointments within 13 months of the first visit will be assessed. We recognized that follow-up recommendations will vary for each patient depending on eye pressure control, medication adherence, disease severity, and surgery/laser appointments. Therefore, the research team, in conjunction with [name] and the CDC, will plan and develop definitions of adherence for patients during Visits 3-8.

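### Table 9's visit quotas do not follow one counting rule: on the natural reading, a patient advised 3-6 months who returns at months 6 and 12 is within the advice but scored non-adherent

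*Combined protocol and SAP*

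**What the plan says.** Section E.2.b sets each year's requirement from the advice given at that year's first visit: "an expected number of visits will be determined based on the recommended follow-up at the first visit for that year". It then fixes the window: "attendance at appointments within 13 months of the first visit will be assessed". It describes the outcome as "attendance at recommended follow-up visits (Visit 4 and later".

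Table 9 turns the advice into a minimum yearly count. Its row for 3-6 month advice reads "At least 3 visits per year with an eye care provider". The corresponding minimums for advice of 1-2, 6 and 12 months are 6, 2 and 1.

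Section E.2.c makes the yearly yes/no result the primary outcome, with one test at Year 1 and one averaged over Years 2 and 3, each at alpha 0.025. Table 6 (column "Appropriate Follow-up Interval (months") and Table 8 keep 3-6 months and 6 months as separate categories, so both rows of Table 9 can be used. Sections C.5.d, C.9 and E.2.b each say that definitions of adherence are still to be developed. None of them gives a counting rule other than Table 9.

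**The concern.** A quota for adherence should pass a patient who does what was advised. Three rows of Table 9 do so for a patient who uses the longest advised interval; the 3-6 month row does not. Two patients with identical visits at months 6 and 12, both within their advice, receive opposite scores: adherent if told 6 months, non-adherent if told 3-6 months.

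E.2.b also does not say expressly whether the year's first visit counts towards the quota. For Year 1 the restriction to Visit 4 and later leaves out Visit 3. For Years 2 and 3 nothing excludes the first visit. This is the scoring rule for the primary outcome, so an inconsistent quota misclassifies compliant patients and dilutes the contrast that Table 10 is powered for.

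**Working it through.** **Inputs.** Quotas 6, 3, 2 and 1 (Table 9). Window of 13 months from the year's first visit (E.2.b). Longest advised intervals of 2, 6, 6 and 12 months (the row labels of Table 9).

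**Step 1: reproduce the quotas.** A patient returning every k months makes floor(13/k) returns, plus 1 if the first visit is counted.

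| Advice (months) | Longest k | Table 9 | Returns only | First visit counted |
|---|---|---|---|---|
| 1-2 | 2 | 6 | floor(6.50) = 6 | 7 |
| 3-6 | 6 | 3 | floor(2.17) = 2 | 3 |
| 6 | 6 | 2 | floor(2.17) = 2 | 3 |
| 12 | 12 | 1 | floor(1.08) = 1 | 2 |

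Returns only gives 6/2/2/1, so only the 3-6 month row disagrees with Table 9. Counting the first visit gives 7/3/3/2, so only the 3-6 month row agrees. A 12-month window gives the same two sets. Neither is 6/3/2/1.

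**Step 2: who is misscored on the returns-only reading.** Three returns in 13 months at a constant interval need k of at most 13/3 = 4.33 months. Within the advised range, the returns made are:
- 3 months: 4
- 3.5 and 4 months: 3
- 4.5, 5, 5.5 and 6 months: 2

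Constant intervals from 4.33 to 6 months fail, which is (6 - 4.33)/(6 - 3) = 56% of the advised range. This is a share of the range, not of patients. As an illustration, assume instead that each interval varies independently and uniformly over 3-6 months. About 38% of fully compliant patients then reach three returns, so about 62% are scored non-adherent.

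**Step 3: if the first visit counted.** Nobody following 3-6 month advice would be wrongly failed. The 12-month quota would be met with no return, the 6-month quota with one of two advised returns, and the 1-2 month quota with five of six returns at 2-month intervals.

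**Step 4: what misclassification could cost.** Table 10 gives 87% power for 50% against 70%. With n = 135 per group and z = 2.241 (two-sided alpha 0.025):
- SE under the null = sqrt(2 x 0.6 x 0.4/135) = 0.0596
- SE under the alternative = sqrt((0.25 + 0.21)/135) = 0.0584
- Power = Phi((0.20 - 2.241 x 0.0596)/0.0584) = Phi(1.14) = 87%, as stated in the plan

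Now assume that a share m of true adherers is scored non-adherent, equally in both arms. The documents give no value for m, so a range is shown.

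| m | Scored rates | Relative risk | Power |
|---|---|---|---|
| 0 | 50% v 70% | 1.40 | 87% |
| 10% | 45% v 63% | 1.40 | 77% |
| 20% | 40% v 56% | 1.40 | 65% |
| 30% | 35% v 49% | 1.40 | 54% |

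To place m: if constant intervals were spread evenly over 3-6 months, m = 20% would need 0.20/0.56 = 36% of true adherers to be on 3-6 month advice.

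**The case against.** **Further definition was planned.** The plan promises adherence definitions in three places, and C.5.d puts that work before the study begins. That shows Table 9 was not meant to be the last word. It does not repair the table, because no other rule is stated.

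**A range needs some cutoff.** Three lies between the 2 and 4 returns that 3-6 months implies, so it could be deliberate. A midpoint rule (12/4.5 = 2.7, about 3) would explain this row, but the same rule gives 12/1.5 = 8 for the 1-2 month row, where Table 9 has 6. No common rule is left, although the choice of cutoff remains partly a matter of judgement.

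**The same rule applies to both arms.** If it misses the same fraction of true adherers in each, the relative risk is preserved and the loss is power. That stands as an assumption. It could fail if navigators (C.8) book visits earlier within the advised range than usual care patients do; the documents do not settle this. The secondary analysis in E.2.e, appointments per person-year, uses no quota and is unaffected.

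**Stronger readings that the documents do not support.**
- A reader might infer that every patient who follows 3-6 month advice fails. Those returning every 3-4 months pass.
- A reader might infer that 12-month patients are adherent by construction in Years 2 and 3, that a visit in month 12-13 is counted in two years, and that the two primary tests certainly use different definitions. These need the first visit to be counted in later years. E.2.b reads more naturally as an anchor visit followed by returns, the 13th month makes sense as grace for a 12-month return, and E.2.e likewise counts appointments after Visit 3. The point that stands is that the text leaves the literal reading open.
- A reader might infer that the 3-6 month row is common. Table 6 uses it when target pressure is not reached without progression, but that table covers primary open-angle glaucoma only, and no section gives the distribution of recommendations.

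**Conclusion.** The concern holds, within limits. No single treatment of the first visit, scored at the longest advised interval, yields 6/3/2/1. On the natural returns-only reading, the 3-6 month row fails compliant patients whose regular intervals exceed 4.33 months, while the other three rows are consistent. The E.2.b wording does not settle the counting of the first visit in Years 2 and 3, so a literal reader could apply one definition at Year 1 and another later.

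The size of the effect on the trial is unknown, because the share of patients on 3-6 month advice and their actual intervals are not given. The power figures are illustrations under assumed, equal misclassification. The defect still merits correction: it sits in the only stated scoring rule for the primary outcome, and the promised definitions do not replace it.

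**What to change.** In E.2.b, state that only return visits after the year's first visit count towards the quota, in every year, within the 13-month window, and that each visit counts as a return in one year only.

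In Table 9, reconcile the 3-6 month row with the other three by scoring every row from the longest advised interval, which gives at least 2 returns for 3-6 months. Fix both before outcome data are seen, and record that they complete the definitions promised in C.5.d, C.9 and E.2.b.

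The cost is one table cell and a sentence or two, with no new data. The small downside is that the 3-6 and 6 month rows then share a quota of 2, so the score no longer separates them. The change concerns outcome scoring only and alters no clinical follow-up interval.

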**Table 10: Determination of Power Calculation**

Percent Adherence Under Usual Care	Percent Adherent Under Enhanced Intervention	Relative Risk	Power
35%	55%	1.57	86%
40%	60%	1.5	86%
45%	65%	1.44	86%
50%	70%	1.4	87%
55%	75%	1.36	89%
60%	80%	1.33	92%

E.2.e. Secondary Analyses for Aim 2: We will perform a secondary analysis to test for differences in the average number of appointments kept per person-year of follow-up. We will use Poisson regression to model

the total number of appointments after Visit 3 by randomization assignment. The offset term will be time under observation measured from Visit 3 to end of follow-up. We will adjust baseline for age, diagnosis, vision impairment, and vision-related quality-of-life. Change in continuous clinical and quality-of-life measures (IOP, visual acuity, NEI-VFQ, etc) will be modeled using mixed effects linear regression. Fixed effects will be time (treated continuously), randomization assignment, treatment by time interaction, age, and diagnosis. A first-order autoregressive correlation structure will be assumed to model correlation among repeated measurements. When possible, random slope and intercept terms may also be included. Effects of intervention on these measures will be tested by the significance of the interaction term.

E.2.f. Exploratory Analyses for Aim 2: We will consider whether the effect of the intervention differs by baseline patient characteristics of glaucoma severity (using VF mean deviation), and vision-related quality-of-life (NEI VFQ score). The primary model will be extended to include the interaction between these variables and randomization assignment to allow for estimation of intervention effects by baseline categories.

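### The Aim 2 primary model lists a randomization-by-treatment interaction, which repeats the arm effect; the two primary tests need randomization by year, so the term should be corrected

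*Combined protocol and SAP*

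**What the plan says.** Section E.2.c describes yearly yes/no adherence over three years and the method: "We will model this longitudinal dichotomous outcome using Poisson regression within a generalized estimating equation (GEE) framework". The terms follow: "Our model will include time (Year 1, 2, and 3), randomization assignment, randomization by treatment interaction, and baseline individual characteristics". The baseline characteristics named are age, diagnosis, vision impairment and vision-related quality of life. No interaction with time is listed, and no other section gives a different primary model.

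The section continues: "Within this model, we will test 2 hypotheses". The first is "First, we will compare randomization groups at Year 1 to test whether there are differences in early adherence". The second is "Second, we will calculate the average effect of randomization across Years 2 and 3 and test the long-term efficacy of the intervention". On error control it says: "Each test will be performed with alpha=0.025".

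Two other places bear on the reading. Section E.2.b says patients are analysed in their randomized group whatever amount of intervention they received. Section E.2.e lists the fixed effects of the secondary mixed model as continuous time, then "randomization assignment, treatment by time interaction, age, and diagnosis".

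**The concern.** An interaction between randomization and treatment has no meaning when both words denote the same two-level variable. Without an arm-by-time term, the model assumes that the relative risk of adherence is identical in Years 1, 2 and 3. The plan's two primary hypotheses exist to separate an early effect from a lasting one, so they need arm effects that can differ by year.

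This is the only statement of the primary model, and both alpha 0.025 tests rest on it. The effect-modification analyses in E.2.f extend the same model, so they inherit the wording.

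**Working it through.** **1. The plan's own figures.** Table 10 gives power of 86, 86, 86, 87, 89 and 92% for usual-care adherence of 35, 40, 45, 50, 55 and 60% with a 20-point gain. Inputs from E.2.d: 135 per group, two-sided chi-square, alpha 0.025 (z = 2.241). The formula is power = Φ{[d − z·√(2·p̄(1−p̄)/n)] / √[(p1(1−p1)+p2(1−p2))/n]}.

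For 40% v 60%: [0.20 − 2.241 × √(2 × 0.25/135)] / √(0.48/135) = (0.20 − 0.1364)/0.0596 ≈ 1.07, so power is 85.7%. The six rows give 86.1, 85.7, 86.1, 87.2, 89.1 and 91.6%, which reproduces the table. The calculation compares two proportions at one time point and does not involve the GEE model, so correcting the interaction term leaves it unchanged.

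**2. The terms as listed.** Let R = 0 or 1 for arm, and Y2 and Y3 be indicators for Years 2 and 3. The listed terms are intercept, Y2, Y3, R and R×R. Because R×R = R, there are 5 columns over the six arm-by-year cells but the rank is 4. What remains is log(risk) = b0 + b2·Y2 + b3·Y3 + b·R, plus covariates.

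- Year 1 arm effect: b.
- Mean of the Year 2 and Year 3 arm effects: (b + b)/2 = b.

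Both hypotheses reduce to the same coefficient.

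**3. The terms with randomization by categorical year.** The columns are intercept, Y2, Y3, R, R×Y2 and R×Y3: 6 columns, rank 6.

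- Year 1: contrast (0, 0, 0, 1, 0, 0).
- Years 2–3 average: contrast (0, 0, 0, 1, 0.5, 0.5).

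These are distinct, and both can be estimated.

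**4. Why time should stay categorical here.** If the continuous time of E.2.e were borrowed, the arm log relative risk would be a + c·t. The Year 1 effect would be a + c and the Years 2–3 average a + 2.5c. The Year 2 effect would be forced to lie midway between those of Years 1 and 3 on the log scale. E.2.c names the three years as levels of time, which points to categories.

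**5. Illustration only.** The yearly rates are assumptions; only the 40% v 60% pair appears in Table 10. With equal numbers in every arm-year cell and an independence working correlation, the common relative risk is the sum of the intervention rates divided by the sum of the usual-care rates. Usual care is 40% each year, a sum of 1.20.

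| Intervention, Years 1/2/3 | True RR, Year 1 | True RR, Years 2–3 | Literal model, both |
|---|---|---|---|
| 60/40/40% | 1.50 | 1.00 | 1.40/1.20 = 1.17 |
| 60/48/44% | 1.50 | √(1.20 × 1.10) = 1.15 | 1.52/1.20 = 1.27 |
| 60/60/60% | 1.50 | 1.50 | 1.80/1.20 = 1.50 |

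A simulation of the first row (400 data sets, 135 per group, exchangeable GEE, assumed latent within-patient correlation 0.4) gave 1.18 from the literal model. The randomization-by-year model gave 1.50 and 1.00. If the effect is constant over time, as in the last row, the two models estimate the same quantity.

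**The case against.** The strongest reply is that this is a one-word slip which the section itself resolves. Both hypotheses are to be tested within this model, so the model must contain arm-by-year terms. E.2.e uses treatment to mean arm and pairs it with time. An analyst who entered a variable multiplied by itself would meet a singular design at once. All of this stands, and it settles what was meant.

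A reader might go further and infer that the plan prescribes a common relative risk, so that an effect that fades would be reported as long-term efficacy. The documents do not support that. The term list and the hypotheses contradict each other, and the hypotheses plainly call for year-specific effects. The fading rates above are not in the plan. Nor can the point be stretched to power or sample size, because Table 10 does not depend on this model.

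The reply does not make the correction unnecessary. This is the sole specification of the primary model, and the intended term does not settle every detail. The only correctly worded interaction, in E.2.e, goes with continuous time. E.2.c also speaks of an overall relative risk for both tests without saying on what scale Years 2 and 3 are averaged. Reading treatment as medical therapy does not help either: no such variable is among the listed terms, and it would not separate Year 1 from Years 2–3.

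**Conclusion.** The interaction term in E.2.c is wrong as written. The listed terms give one arm effect for all years and contradict the two primary hypotheses that the same section tests within the model. It is very probably a wording slip for randomization by time.

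The algebra needs only that randomization and treatment are the same variable, which follows from the as-randomized analysis in E.2.b. The stated power, sample size and alpha split are unaffected. The relative risks of 1.17 and 1.27 show what the literal model would give under assumed rates; they are not a forecast of bias in this trial. The correction should be made because both primary tests depend on this line, but the point is one of specification and does not show that the design is unsound.

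**What to change.** In E.2.c, replace the randomization-by-treatment term with a randomization-by-time interaction, and state that year is categorical with three levels, unlike the continuous time of the secondary model in E.2.e. Define the two primary contrasts:

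- Year 1: the arm log relative risk in Year 1.
- Years 2–3: the mean of the Year 2 and Year 3 arm log relative risks, exponentiated for reporting.

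Say that the E.2.f analyses extend this corrected model. The cost is a line or two of text, best settled before outcome data by arm are examined. It needs no new data, has no effect on patients, and leaves Table 10, the sample size and the alpha split as they are.

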C.5.a. Case Findings/Outreach/ Recruitment: The proposed intervention has been planned and developed to detect glaucoma, other eye diseases, and functional vision loss. A significant initiative has already taken place within our partner organizations by our WETD to inform all referring PCPs about the locations where fundus photographs are taken for their patients with diabetes. Ongoing referrals have been successfully generated but only 50% of those patients scheduled show up for the detection exam. Therefore, all participants will receive reminder phone calls and letters as part of our recruitment and retention strategies.

Community partners' quality control and information technology staff have agreed to provide patient reports at each practice using the inclusion criteria. Using these lists, we will adopt "opt-out" recruitment methods so we can call all patients to describe the study, confirm eligibility, and schedule them for the detection exam (Visit 1). We will also develop customized, linguistically appropriate flyers for waiting rooms. We will submit all of these documents with our initial IRB applications at each partner institution so there are no delays in initiating recruitment. We will work with each partner's medical director to develop these materials. All eligible patients who are scheduled for Visit 1 will receive a personal phone call to remind them of the appointment, discuss the importance of attending this visit, and answer any questions. Many patients lack knowledge regarding the permanency of vision loss due to glaucoma and diabetes and even perceive that it is not important to attend all follow-up visits. Therefore, our study staff will continue to educate patients through phone calls and personal contact. A total of up to 3 attempts will be made in total to schedule or reschedule cancelled/no-show appointments.

C.5.b. Inclusion/Exclusion Criteria: The targeted, diverse, at-risk populations for the implementation research are people with previously undiagnosed glaucoma or glaucoma suspect, other eye diseases, and vision loss.

*Inclusion Criteria:*

- African-American, Hispanic, or Asian individuals over age 40
- Caucasian individuals over age 65
- Individuals of any ethnicity, over age 40 with a family history of glaucoma

- Individuals of any ethnicity, over age 40 with diabetes
- Individuals who meet one of the above criteria who have not seen an ophthalmologist in the past year

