E.1.c. Data Management/Quality Assurance: Exam results and treatment dates will be linked with MRNs and stored in a password-protected, encrypted, hard drive. The biostatistician and data manager, using SAS software, will create a separate list linking patient names and exam and treatment dates. To track follow-up adherence and scheduling, we will document on EPM the exam/treatment dates. We will also note the number of follow-up visits that each patient schedules, keeps, reschedules, cancels, and misses. The project manager will also monitor and store results, such as the NEI VFQ-25 and the satisfaction survey. De-identified, aggregated data will be sent to Westat in an Excel spreadsheet. Upon completion of the project, all data and databases will be securely housed for 3 years. Wills Eye Hospital will maintain the confidentiality of records according to the provisions of Title 42 of the Code of Federal Regulations, Part II. (See Table 8)

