### Table 8: Process Measures to Be Tracked

Process Measures	Phase 1 Plan, Develop Detection	Phase 2 Confirm Diagnosis Follow-up	Phase 3 Follow-Up Disseminate Replicate
# of partners and primary care offices for recruitment sites	✓		
# of patients received by each primary care offices and health centers	✓		
# of letters mailed/calls made to patients from recruitment and Visit 1	✓		
# of patients scheduled, confirmed, attended detection eye exam Visit 1-2	✓	✓	
# of patients who cancelled and assessment of barriers to attending exam	✓	✓	✓
# of patients/doctors sent letters with normal/abnormal eye exam results	✓	✓	✓
# of patients diagnosed with glaucoma, suspect, and other eye diseases	✓	✓	✓
# of patients who attended exams with an ophthalmologist (Visits 3-8)		✓	✓
# of patients recommended to follow-up in 1-2 weeks, 1-2 months, 3-6 months, 6 months, and 12 months from baseline Visits 2-8		✓	✓
# of people prescribed ocular medication, laser therapy, or eye surgery		✓	✓
# of patients who requested medication assistance for eye drops	✓	✓	✓
# of patients who requested and used translation/interpreter services	✓	✓	✓
# of patients who requested and used transportation services	✓	✓	✓
# of referrals for a low-vision specialist, cataract surgeon, etc.		✓	✓
# of referrals for a Medicare/Medicaid advisor or to complete application		✓	✓

**E.1.d. Patient Satisfaction Surveys:** With Westat, the CDC and Advisory Board members, we will develop brief questions regarding the patient's satisfaction. We will survey patients at the conclusion of all visits. Wills Eye research staff will administer surveys during the detection and baseline visits. We hypothesize that satisfaction will be greater for those in the intervention group than in the usual care group.

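### The primary and appointment-count models name no measure of appointment-keeping before randomisation; adding one would give a small precision gain, about 0 to 3 power points under assumed correlations

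*Combined protocol and SAP*

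**What the plan says.** E.2.b defines the Aim 2 outcome as "attendance at recommended follow-up visits (Visit 4 and later"), summarised by year. E.2.c states: "We will model this longitudinal dichotomous outcome using Poisson regression within a generalized estimating equation (GEE) framework". The model contains year, arm, their interaction and "baseline individual characteristics believed to be associated with adherence to follow-up, including age, diagnosis, vision impairment, and overall vision-related quality-of-life". Two comparisons are made, Year 1 and the average of Years 2 and 3: "Each test will be performed with alpha=0.025".

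E.2.e adjusts the count of appointments kept for age, diagnosis, vision impairment and vision-related quality of life, with no wording that leaves the list open.

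On attendance before randomisation:

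- Table 8 counts the number "of patients scheduled, confirmed, attended detection eye exam Visit 1-2", and also counts cancellations in all three phases.
- E.1.c records "the number of follow-up visits that each patient schedules, keeps, reschedules, cancels, and misses".
- C.5.a, on recruitment to Visit 1, says: "A total of up to 3 attempts will be made in total to schedule or reschedule cancelled/no-show appointments".
- C.9 randomises patients after a completed Visit 2. The note in C.5.c lets patients with elevated eye pressure skip Visit 2 and be randomised at Visit 1.

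**The concern.** A baseline version of the outcome is often among the most useful covariates in a randomised comparison. Here the outcome is whether patients keep appointments, and each patient has been given at least one study appointment, normally two, before being randomised. Cancelled or missed appointments on the way to those visits are a direct, if crude, measure of the same behaviour. They fit E.2.c's own criterion for a covariate, yet neither model names them.

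Adjustment would be legitimate. Visits 1 and 2 come before randomisation and lie outside the outcome, which starts at Visit 4. With a log link and no interaction between arm and the covariate, the relative risk is collapsible, so the quantity estimated stays the same. What is at stake is precision in both primary tests and removal of any chance imbalance on this variable. Validity is not at stake.

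**Working it through.** **Inputs.** From E.2.d: 150 randomised per group, 10% dropout, so 150 × 0.9 = 135 analysed per group; a 20-point difference; power calculated "using a two-sided chi-square test with alpha=0.025". From C.4.a: 187 per group, which differs from E.2.d. The correlation (rho) between earlier and later appointment-keeping is not in the documents. I take 0.1 to 0.3 as an assumption, meaning the correlation that remains after the four named covariates.

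**Step 1: reproduce Table 10.** With p̄ = (p1 + p2)/2 and z = 2.2414 (two-sided 0.025):

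power = Φ{[|p2 − p1| − z√(2p̄(1 − p̄)/n)] / √([p1(1 − p1) + p2(1 − p2)]/n)}

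For 40% v 60% and n = 135: [0.20 − 2.2414 × √(0.50/135)] / √(0.48/135) = (0.20 − 0.1364)/0.05963 = 1.066, so power is 85.7%.

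| Usual care v intervention | Table 10 | Recomputed |
|---|---|---|
| 35% v 55% | 86% | 86.1% |
| 40% v 60% | 86% | 85.7% |
| 45% v 65% | 86% | 86.1% |
| 50% v 70% | 87% | 87.2% |
| 55% v 75% | 89% | 89.1% |
| 60% v 80% | 92% | 91.6% |

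All six rows agree.

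**Step 2: add the covariate.** Adjustment multiplies the variance by about 1 − rho², so the effective n is n/(1 − rho²). For rho = 0.3: 135/0.91 = 148.4. For 40% v 60%:

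| rho (assumed) | Effective n from 135 | Power | Effective n from 187 | Power |
|---|---|---|---|---|
| 0 | 135.0 | 85.7% | 187.0 | 95.2% |
| 0.1 | 136.4 | 86.1% | 188.9 | 95.4% |
| 0.2 | 140.6 | 87.2% | 194.8 | 95.9% |
| 0.3 | 148.4 | 89.0% | 205.5 | 96.8% |

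The gain is 0.4 to 3.3 points at 135 per arm and 0.2 to 1.6 points at 187. The 187 columns make no allowance for dropout.

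**Step 3: is that range of rho reasonable for a yes/no marker?** Suppose 20% to 50% of patients have an earlier miss, later adherence among them is 0.8 to 0.5 times that of the others, and overall adherence is 40% to 50%. All of these are assumptions. Rho then runs from about 0.07 to 0.33, and effective n rises by 0.5% to 12.5%.

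**Step 4: cross-check by simulation.** Single-year Poisson regression with robust variance, 135 per arm, 40% v 60%, 1,500 trials per scenario (Monte Carlo error about 0.9 power points), without and with the marker:

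| Share with a miss | Adherence ratio | Mean SE of log RR | Power |
|---|---|---|---|
| 20% | 0.8 | 0.1274 → 0.1270 | 86.7% → 86.6% |
| 20% | 0.5 | 0.1272 → 0.1241 | 84.9% → 86.3% |
| 50% | 0.65 | 0.1273 → 0.1246 | 84.1% → 85.8% |
| 50% | 0.5 | 0.1277 → 0.1210 | 86.9% → 91.5% |

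The standard error falls by about 0.3% to 5%. The largest gain needs both the highest prevalence and the strongest association. None of these runs includes the four covariates already in the plan's model.

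**The case against.** The strongest reply is that nothing here is broken. E.2.c's list is open and prior attendance fits its rule, so the covariate is unnamed rather than ruled out. Table 10 already shows 86% to 92% power. Both statements stand. They do not reach E.2.e, where the list is fixed, and an open list for a primary model should in any case be closed before outcomes are seen.

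A reader might infer that the study already holds this variable for each patient and that using it is free. The documents do not support that. Table 8 lists counts of patients, and the per-patient record in E.1.c is worded for follow-up visits. The limit on scheduling attempts in C.5.a and the tracking of cancellations from Phase 1 imply patient-level scheduling records, but no section states it.

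A reader might also infer a large gain. At rho 0.5 the same formula gives 94.4% power at 135 per arm, nearly 9 points up. Nothing in the documents supports that value, for four reasons:

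- The 50% attendance in C.5.a describes existing diabetes referrals and is given as the reason for adding reminders. The 20% in C.2.b comes from another project. Neither describes randomised patients, who by the ordinary route have attended both visits.
- C.5.a's limit covers scheduling and rescheduling together, which further narrows the variation.
- The 85.7% starting point is an unadjusted chi-square test. The planned model already has four covariates, so only the remaining correlation counts.
- Attending a free examination at one's own primary care site after reminder calls differs from meeting yearly visit counts with outside providers over three years.

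In favour of the change, a few points can matter if the effect is smaller than planned. The navigator trial in C.3.b found 48% v 30% attendance. At 135 per arm that gives 78.9% power, rising to between 79.4% and 83.0% for rho 0.1 to 0.3. That trial measured attendance at one appointment, so the comparison is only indicative.

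**Conclusion.** The point holds as an optional improvement. Neither model names appointment-keeping before randomisation, which is a valid covariate and the nearest baseline analogue of the outcome. The likely benefit is about 0 to 3 power points at 135 per arm and less than 2 points at 187. It rests on an assumed residual correlation of 0.1 to 0.3 and on the marker being derivable per patient. The gain could be close to zero if earlier and later attendance are only weakly related. The omission introduces no bias, does not invalidate the tests and does not make Table 10 wrong.

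**What to change.** First confirm that scheduling records allow a per-patient marker for Visits 1 and 2. If they do:

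- Add to the covariates in both E.2.c and E.2.e: any Visit 1 or Visit 2 appointment cancelled or missed before randomisation (yes/no). Close the E.2.c list at the same time.
- For patients randomised at Visit 1, use the Visit 1 record only and include an indicator for this route, because they had fewer appointments to miss.
- State that Visit 3 attendance is not to be used as a covariate, since it comes after randomisation and may be affected by the intervention.

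The cost is a short wording change, a small data derivation and one model parameter for the marker, plus the indicator for the Visit 1 route. No extra data collection is needed if the scheduling records are kept by patient. The randomised number (300 in E.2.d, 374 in C.4.a) should be reconciled separately, because it affects power more than this covariate is likely to.
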